3. STUDY DESIGN

3.1 DESCRIPTION OF THE STUDY

[figure not shown]
The study is designed as a multi-site, prospective, 15-month longitudinal, cohort study measuring CSF mHTT in patients with early manifest Stage I or Stage II HD. After completion of the observational period, participants will have the option of receiving the active compound RO7234292 in an OLE study (Study BN40955, ClinicalTrials.gov Identifier NCT03842969), provided they meet eligibility criteria, the data from the ongoing RO7234292 program supports continued development, and subject to approval by the relevant competent authorities and Institutional Review Boards/Ethics Committees (IRBs/ECs).

This study will enroll up to approximately 100 patients at approximately 20 sites. After a 28-day screening period, patients will return to the clinic at baseline and at Months 3, 9, and 15. During these visits, patients will receive clinical, MRI, and Roche HD mobile app assessments; they will also provide CSF and blood samples. Patients who will not enter the OLE study (Study BN40955, ClinicalTrials.gov Identifier NCT03842969) will have a post-observational follow-up visit 2 weeks after the 15-month longitudinal period that may occur by telephone or in the clinic. Early termination visits should take place via clinic visit, where possible. If there is the occurrence of a failed CSF collection procedure due to inadequate establishment of access to the IT space, there may be a second attempt up to 14 days after the original attempt. For this additional visit, local laboratory analysis of coagulation factors (INR and/or PT, aPTT) and platelets must be conducted and the results reviewed within 72 hours prior to performing the LP. In addition, neurological examination, vital signs, and a review of AEs and concomitant medication should occur as part of the safety and tolerability evaluations on the day of LP.

The final study visit will be Study Day 421 (Month 15) for patients who enter the OLE Study (Study BN40955, ClinicalTrials.gov Identifier NCT03842969), and the follow-up visit will be the final study visit for those patients who do not enter the OLE.

[Figure 1](#) presents an overview of the study design, with 1 month defined as one 28-day period. A schedule of activities is provided in [Appendix 1](#).

Figure 1 Study Schema

HD=Huntington's disease.

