4.6.3 Site Discontinuation

The Sponsor has the right to close a site at any time. Reasons for closing a site may include, but are not limited to, the following:

- Excessively slow recruitment

- Poor protocol adherence
- Inaccurate or incomplete data recording
- Non-compliance with the International Council for Harmonisation (ICH) guideline for Good Clinical Practice or any other pertinent local law or guideline
- No study activity (i.e., all patients have completed the study and all obligations have been fulfilled)

5. **ASSESSMENT OF SAFETY**

5.1 **SAFETY PLAN**

After informed consent has been obtained and after the initiation of study procedures, both adverse events and serious adverse events related to a study procedure will be reported until the last clinic visit.

5.2 **SAFETY PARAMETERS**

Since no study medication will be given to the patients, safety assessments will consist of monitoring and recording adverse events, including serious adverse events related to study procedures.

5.2.1 **Adverse Events**

According to the ICH guideline for Good Clinical Practice, an adverse event is any untoward medical occurrence in a clinical investigation subject administered a pharmaceutical product, regardless of causal attribution.

In the case of this non-drug study, any untoward medical occurrence in a clinical investigation subject that is related to a protocol-mandated intervention is considered an adverse event (e.g., invasive procedures such as *lumbar punctures*).

5.2.2 **Serious Adverse Events (Immediately Reportable to the Sponsor)**

A serious adverse event is any adverse event that meets any of the following criteria:

- Is fatal (i.e., the adverse event actually causes or leads to death)
- Is life threatening (i.e., the adverse event, in the view of the investigator, places the patient at immediate risk of death)

This does not include any adverse event that, had it occurred in a more severe form or was allowed to continue, might have caused death.

- Requires or prolongs inpatient hospitalization (see Section 5.3.5.8)
- Results in persistent or significant disability/incapacity (i.e., the adverse event results in substantial disruption of the patient's ability to conduct normal life functions)
- Significant medical event in the investigator's judgment (e.g., may jeopardize the patient or may require medical/surgical intervention to prevent one of the outcomes listed above)

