5.3.1 Adverse Event Reporting Period

Investigators will seek information on adverse events related to a protocol-mandated intervention at each patient contact. All adverse events related to a protocol-mandated intervention, whether reported by the patient or noted by study personnel, will be recorded in the patient's medical record and on the Adverse Event eCRF *until the patient's last visit or withdrawal*.

After informed consent has been obtained, serious adverse events caused by a protocol-mandated intervention (e.g., invasive procedures such as *lumbar punctures*) should be reported (see Sections 5.4–5.6 for instructions for reporting serious adverse events) until the patient's last visit or withdrawal.

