Appendix 1 Schedule of Activities (cont.)

Study Day	Screening Period	Observational Period						Follow-Up (or Early Termination) ^a
	Days -29 to -2	Day -1 to 1 (Baseline)	Day 85 (Month 3)	Day 169 (Month 6)	Day 253 (Month 9)	Day 337 (Month 12)	Day 421 (Month 15)	
Visit Window (days)			±7	±10	±7	±10	±7	
Type of visit	CL	CL	CL	PH	CL	PH	CL	CL or PH
Adverse events ^t	x	x	x	x	x	x	x	x
Concomitant medications ^u	x	x	x	x	x	x	x	x

CL = clinic; ClinROs = clinician-reported outcomes; CSF = cerebrospinal fluid; C-SSRS = Columbia-Suicide Severity Rating Scale; eCRF = electronic Case Report Form; HBsAg = hepatitis B surface antigen; HCV = hepatitis C virus; HD = Huntington disease; MRI = magnetic resonance imaging; ObsROs = observer-reported outcomes; PerfOs = performance outcomes; PH = phone; PROs = patient-reported outcomes; RBR = Research Biosample Repository.

- ^a Post-observational follow-up visit will take place 2 weeks after end of observational period and will occur via clinic visit or by telephone call. Early termination visit should occur via clinic visit where possible.
- ^b Capacity to consent assessment (patient only) and informed consent (for both the patient and study companion [if available]).must be documented before any study-specific screening procedure is performed and may be obtained more than 28 days before baseline visit. A maximum of one re-screening will be allowed within 8 weeks of the initial screening failure for patients who fail the initial screening (e.g., as a consequence of abnormal laboratory values or general medical status not meeting inclusion or exclusion criteria). If re screening is required, central CAG repeat length testing from the initial screening does not need to be repeated, and the screening MRI and viral serology from the initial screening may be acceptable as part of the re screening assessments if performed within 12 weeks of the baseline visit.
- ^c Includes measurements of respiratory rate, pulse rate, and systolic and diastolic blood pressure while the patient is in a seated position after resting for approximately 5 minutes, and temperature. Record abnormalities observed at baseline on the General Medical History and Baseline Conditions eCRF.
- ^d Height in meters.
- ^e Weight in kilograms.

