## 2. STUDY DESIGN

This study will enroll up to approximately 100 patients at approximately 20 sites. After a 28-day screening period, patients will return to the clinic at baseline and at Months 3, 9, and 15. During these visits, patients will receive clinical, magnetic resonance imaging (MRI), and Roche HD mobile app assessments; they will also provide CSF and blood samples. A post-observational follow-up visit will take place 2 weeks after the 15-month longitudinal period and may occur by telephone or in the clinic.

[Figure 1](#) presents an overview of the study design, with 1 month defined as one 28-day period. For further details, see Section [4.2](#) of the protocol.

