#### **4.7.2        Adverse Events**

Since no study medication will be given to the patients, safety assessments will consist of monitoring and recording adverse events, including serious adverse events, related to study procedures.

Adverse events and SAEs related to a study procedure reported from date of informed consent until the patient's last visit or withdrawal, will be analyzed.

All AE will be listed, any AE which starts after the reference time point (see Section 4) will be summarized.

The number of unique patients who experience and report an adverse event, each adverse event, and the number of adverse events themselves will be tabulated by medical dictionary for regulatory activities (MedDRA) System Organ Class and Preferred Term. Adverse events will also be summarized by severity.

Serious AEs, AEs that lead to study discontinuation and deaths will also be analysed separately. Selected adverse events may be summarized and listed separately.

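### For patients who enter the OLE, adverse event recording ends at the visit of the fourth lumbar puncture, so non-serious events of that puncture with later onset are not counted

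*Protocol*

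**What the plan says.** Protocol 4.5.6 and Appendix 1 place LPs at baseline and at Months 3, 9 and 15. On the last of these, Protocol 3.1 says: "The final study visit will be Study Day 421 (Month 15) for patients who enter the OLE Study". Patients who do not enter the OLE "will have a post-observational follow-up visit 2 weeks after the 15-month longitudinal period that may occur by telephone or in the clinic". In Appendix 1 the follow-up column is marked for AEs and concomitant medications and for nothing else.

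Under Protocol 5.3.1, AEs related to a protocol-mandated intervention are recorded "until the patient's last visit or withdrawal". SAP 4.7.2 matches this: procedure-related AEs "reported from date of informed consent until the patient's last visit or withdrawal, will be analyzed". Beyond that point, Protocol 5.6 asks only for serious events believed to be procedure-related that come to the investigator's attention. Protocol 5.5.1 follows known events to resolution or stability, but opens no period for new ones.

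The sections are not worded alike.

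- **Who has the follow-up.** Appendix 1 footnote a ("Post-observational follow-up visit will take place 2 weeks after end of observational period") and SAP Section 2 ("A post-observational follow-up visit will take place 2 weeks after the 15-month longitudinal period") carry no OLE exception. Protocol 3.1 does.
- **When AE reporting ends.** Protocol 5.1 says "both adverse events and serious adverse events related to a study procedure will be reported until the last clinic visit". Protocol 5.3.1 ends it at the last visit, of whatever type.

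**The concern.** The study gives no drug, so its safety record consists mainly of AEs caused by study procedures, and LP is the protocol's own example of such a procedure. The fourth LP falls on the day AE recording closes for OLE entrants. MRI and the in-clinic outcome assessments should come before the LP (Protocol 4.5.8 and 4.5.10), so little of the visit remains after it. A non-serious event that begins that evening or in the following days has no place in the record. Neither document says that the OLE passes such events back.

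At stake are the AE counts and the number of patients with an AE. Both would be too low, and ascertainment would be less complete in OLE entrants than in other patients.

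**Working it through.** **1. The plan's own dates.** Protocol 3.1 gives the visit schedule "with 1 month defined as one 28-day period". Month 15 is 15 x 28 + 1 = Day 421, as stated. The two-week follow-up is Day 421 + 14 = Day 435, and (420 + 14)/28 = 15.5 months, which matches the expected end of study in Protocol 3.2.

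**2. Time from each LP to the next scheduled AE contact** (nominal days from Appendix 1, including the telephone visits):

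| LP | Next contact, OLE entrants | Days | Next contact, others | Days |
|---|---|---|---|---|
| Day 1 | Day 85 | 84 | Day 85 | 84 |
| Day 85 | Day 169 | 84 | Day 169 | 84 |
| Day 253 | Day 337 | 84 | Day 337 | 84 |
| Day 421 | none | 0 | Day 435 | 14 |

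A repeat LP after a failed attempt, up to 14 days later, moves the last contact, but AE review is then on the day of that LP. An MRI rescan more than 3 days after the LP could add a contact. Neither is routine.

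**3. Share of LPs with no later contact.** Let f be the share of patients who enter the OLE (not given, so assumed), with all four LPs done. One LP in four is affected in each entrant, so the share is f/4. With 100 patients and 400 LPs:

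- f = 25%: 25 LPs, 6.25%
- f = 50%: 50 LPs, 12.5%
- f = 75%: 75 LPs, 18.75%
- f = 100%: 100 LPs, 25%

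**4. Share of events lost.** Let d be the share of fourth-LP events that are non-serious and start after the visit (also assumed). With equal event rates per LP, and all other LP events captured, the undercount is f x d/4.

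- f = 50%: 0.5 x 0.25/4 = 3.1% to 0.5 x 0.9/4 = 11.3%
- f = 100%: 0.25/4 = 6.25% to 0.9/4 = 22.5%

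The ceiling, at d = 1, is f/4.

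**5. Patient-level illustration for an OLE entrant.** Assume an AE risk p = 10% per LP, independent between LPs. The true four-LP incidence is 1 - 0.9^4 = 34.4%. The recorded incidence is 1 - 0.9^3 x [1 - 0.1(1 - d)]:

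- d = 0.25: 32.6%
- d = 0.5: 30.7%
- d = 0.9: 27.8%

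**The case against.** The strongest reply is that the loss is narrow and the stakes are modest. Only non-serious events with onset after the visit are missed. No objective concerns safety, and Protocol 6.5 promises only limited safety analyses. The SAP plans no AE comparison of OLE entrants with others. The first three LPs have no scheduled contact for 84 days, so they are not a benchmark of complete capture either. All of this stands and limits the weight of the point, but it does not close the gap.

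Much of the inconsistent wording can also be explained. Footnote a says when and how the follow-up happens, not who has it. SAP Section 2 appears to follow older text: its synopsis in SAP Appendix 1 is from protocol version 2 (Germany), while the protocol is now version 3. These are matters of alignment.

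Three stronger readings are tempting, and the documents do not support them.

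- **A reader might infer that the SAP will present the fourth LP as fully followed up.** SAP 4.7.2 plans no AE table by LP or visit. It tabulates overall by System Organ Class, Preferred Term and severity, so no Month 15 denominator exists to mislead.
- **A reader might take f/4 as the expected undercount.** It is a ceiling, which assumes that no fourth-LP event starts before the patient leaves.
- **A reader might conclude from Protocol 5.1 that patients followed up by telephone also lose the window.** Protocol 5.3.1, 5.4.2, Appendix 1 footnote t and SAP 4.7.2 all refer to the last visit, and the follow-up column marks AEs for a clinic or telephone contact. The wording of 5.1 needs correcting, but it does not establish that loss.

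**Conclusion.** The gap is real. Followed as written, the plan does not record or analyse non-serious procedure-related AEs that start after an OLE entrant leaves the Day 421 visit. The direction, an undercount in the overall AE tables with less complete ascertainment in OLE entrants, follows from the text.

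The size does not follow from the text. OLE uptake, AE rate per LP and onset times are not given. The ranges in steps 4 and 5 of the working are illustrations under assumed f, d and p. The primary and secondary analyses of mHTT, clinical outcomes, biomarkers and MRI are untouched. This should be corrected, but it does not threaten the study's main conclusions.

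**What to change.** - **Extend the AE period.** In Protocol 5.3.1 and SAP 4.7.2, carry AE recording past the Month 15 LP for OLE entrants by applying to them the two-week telephone AE contact already in Appendix 1. AE data from the OLE could serve instead only if that study is confirmed to record these events. The documents here do not show that it does.
- **Reconcile the wording.** Align Protocol 3.1, Appendix 1 footnote a and SAP Section 2 on who has the follow-up. Align Protocol 5.1 with 5.3.1 on whether reporting ends at the last clinic visit or the last visit.
- **If data collection is complete,** state in the report that the fourth LP in OLE entrants has no AE follow-up after the visit. A table of AEs by preceding LP is optional.

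The cost is one short call per OLE entrant and minor wording changes.

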3.2 END OF STUDY AND LENGTH OF STUDY

The end of the study will be the date from which the last patient, last visit is recorded in the study database. The end of the study is expected to occur 15.5 months after the last patient is enrolled.

The total length of the study, from screening of the first patient to the end of the study, is expected to be approximately 27 months. In addition, the Sponsor may decide to terminate the study at any time.

3.3 RATIONALE FOR STUDY DESIGN

There are currently no longitudinal CSF mHTT data in patients with HD. This study has been designed to collect data for CSF mHTT, other biomarkers, clinical assessments, and the Roche HD mobile app assessments at four timepoints over 15 months.

3.3.1 Rationale for Patient Population

Patients with early-stage HD, defined as Stage I or II by Shoulson and Fahn (1979), will be included in this study, as they are expected to show progressive decline in clinical parameters measurable over a \geq 12-month timeframe (Huntington Study Group 1996; Schobel et al. 2017), and because they have measurable abnormalities in the key biomarkers in cross-sectional studies compared to controls and prodromal individuals (e.g., for CSF mHTT [Southwell et al. 2015; Wild et al. 2015]) as well as longitudinal differences on other outcomes (e.g., for NfL, brain atrophy, and clinical endpoints [Byrne et al. 2017]). The population also represents the stage of manifest HD that might be more plausibly reversed or slowed in response to a therapeutic intervention versus more advanced patients with more neurodegeneration present at baseline who experience less longitudinal decline in clinical parameters such as the TFC score (Penney et al. 1990). Since this population overlaps with the population targeted for the upcoming clinical efficacy studies of the RO7234292 development program, the natural history study will provide useful comparative data.

3.3.2 Rationale for Clinical Assessments

3.3.2.1 Patient-Reported, Clinician-Reported, Observer-Reported, and Performance Outcome Questionnaires

Individuals with HD exhibit a triad of motor, cognitive, and behavioral/psychiatric symptoms that contribute to clinical progression and/or morbidity and quality of life.

A recent survey of patients and caregivers/companions reported executive function/cognitive decline, chorea movement/balance, and depression/apathy as the most impactful symptoms (Simpson et al. 2016).

A comprehensive battery of patient-, clinician-, observer-reported, and performance outcome assessments (PRO, ClinRO, ObsRO, and PerfO, respectively) will be used to document changes over time. The proposed endpoint strategy captures measures known to be sensitive to clinical progression from a clinician and patient perspective, as well as assessments solicited by companion/caregiver report.

The Unified Huntington's Disease Rating Scale (UHDRS) is a collection of assessments commonly used to assess disease status (including symptoms and their impact) and progression in patients with HD (Huntington Study Group 1996). The individual scales of the UHDRS include the TFC score; the highly correlated Independence and Functional Assessment Scales; the TMS; SDMT; SWR; verbal fluency test; and a behavioral assessment. The cUHDRS is a composite of weighted subcomponents of the UHDRS, which also covers multiple domains (motor, cognitive, and functional) and possesses greater sensitivity to detect longitudinal change compared to the UHDRS or its individual subtests (Schobel et al. 2017).

Apathy, depression, anxiety, and irritability are core behavioral symptoms associated with HD (Simpson et al. 2016). The Apathy Evaluation Scale (AES) is a widely used and valid measure of apathy. To assess change in other behavioral symptoms, a newly developed scale, the Symptoms of Major Depressive Disorder Scale (SMDDS), will be used to capture depressive symptoms as well as irritability and anxiety. This scale was selected for its excellent coverage of these core symptoms.

To complement the PerfO measures of cognition (SDMT and SWR), the Quality of Life in Neurological Disorders (Neuro-QoL) Cognition Function Short Form assesses self-reported issues with cognition, such as slow thinking or difficulty learning new tasks.

Speech difficulty is a common issue (with both cognitive and motor deficits impacting ability) and will be measured by a novel single-item measure, the Huntington's Disease–Speaking Difficulty Item (HD-SDI).

The clinician will complete a Clinical Global Impression of Severity (CGI-S) at baseline and a Clinical Global Impression of Change (CGI-C), and the patient will complete the Patient Global Impression of Severity (PGI-S) and the Patient Global Impression of Change (PGI-C).

Concepts such as health-related quality of life (HRQoL), health state utilities, and societal impacts (e.g., work productivity) are of particular interest to European Health Technology Assessment agencies. The WHO Disability Assessment Schedule 2.0 (WHODAS 2.0) and the EuroQol 5-Dimension, 5-Level (EQ-5D-5L) Questionnaire will assess HRQoL and health state utilities, respectively. The Work Productivity and Activity Impairment (WPAI) Scale will capture changes in employment status, including a reduction of work hours or loss of productivity.

Further details on these assessments are included in Section [4.5.10](#).

3.3.2.2 Roche Huntington's Disease Mobile App

The Roche HD mobile app collects sensor data from smartphones and wrist-worn wearables. Smartphones and wrist-worn wearables have high-quality sensors that enable remote, non-invasive, frequent, and precise measurement of motor and non-motor symptoms. Such technology has been used previously in Parkinson disease (Maetzler et al. 2013; Arora et al. 2015; Ossig et al. 2016) and HD (Andrzejewski et al. 2016; Dinesh et al. 2016).

Several cognitive and motor measures sensitive to symptom progression in early HD (Tabrizi et al. 2012) lend themselves to sensor-based measurement. Fine motor impairments can be measured using touch sensors (e.g., circle tracing [Say et al. 2011] and speeded tapping [Tabrizi et al. 2012]). Gait and balance have previously been successfully captured using wearable sensors (Dalton et al. 2013; Andrzejewski et al. 2016; Dinesh et al. 2016), as has choreatic movement in HD patients (Reilmann et al. 2011; Kegelmeyer et al. 2017).

Patients will be asked to complete daily "active" tests and then carry the devices with them as they go about their daily routines (i.e., "passive monitoring"). The collected sensor data will be correlated with traditional clinical assessments as mentioned above and will be used to track the longitudinal trajectory of motor, cognitive, behavioral, and functional parameters.

3.3.3 Rationale for Biomarker Assessments

3.3.3.1 Cerebrospinal Fluid Biomarkers

Measurement of protein levels in the CSF offers the potential to monitor molecular changes that take place in the CNS. A toxic gain-of-function mechanism of mHTT is widely considered to be the primary driver of disease pathophysiology in HD (Wild and Tabrizi 2017). mHTT protein in human CSF is associated with disease stage and severity and with markers of neuronal damage, including CSF NfL and CSF tau levels (Wild et al. 2015). NfL levels in CSF predict progressive MRI measures of brain atrophy, as well as progressive clinical decline in patients (Wild and Tabrizi 2017). Longitudinal analysis of CSF mHTT, NfL, and other biomarkers related to HD, neurodegeneration, and inflammation will facilitate understanding of HD pathophysiology and progression.

